# **Background and rationale**

Autonomic nervous system activity can be measured using heart rate variability (HRV); in brief, as we inhale heart rate increases and, as we exhale, heart rate decreases. HRV is essentially the gap or difference (variation in the time interval between heartbeats), hence a greater/higher HRV is more favourable in relation to health. Researchers have found breathing at 5-6 breath cycles per minute (bcpm) with equal inhalation/exhalation results in electrical rhythms of brain, heart and lungs synchronising — and that this breathwork technique (called 'coherent breathing') optimises HRV, translating into healthy autonomic responses to changes in breathing and thus a more resilient stress-response system (Brown & Gerbarg, 2012). However, despite over two decades of research, there are no well-controlled studies exploring coherent breathing's effects on mental health. We plan to complete the first robust randomised-controlled trial (RCT) comparing coherent breathing to a well-designed placebo.

The theoretical rationale for our study is identifying ways in which coherent breathing exerts its effects via a well-designed RCT within the general population. An appropriate breathwork placebo could help disentangle effects of coherent breathing (Sevoz-Couche & Laborde, 2022). The practical rationale is using the data and information collected to help develop time- and cost-effective remote interventions for lowering stress and improving well-being. This will build upon our previous work; a systematic review and meta-analysis on breathwork and mental health ([name] et al., 2023). We found significant small-medium effects, denoting breathwork was associated with lower levels of stress, anxiety and depression, compared to non-breathwork RCTs. Using the Cochrane Collaboration's latest tool for assessing risk of bias in randomised trials, all the RCTs that were included in our meta-analysis were deemed as being at moderate or high risk of bias, hence we wish to carry out the first robust breathwork RCT with low risk of bias. We want to share our findings through publication in a reputable open-access journal to inform practice and hopefully benefit others.

# **Objectives and endpoints**

The main question that our study attempts to address is: Does coherent breathing lead to improved mental health and wellbeing in a general population adult sample in comparison to a well-designed placebo control?

# **Study hypotheses**

# Primary hypothesis

Coherent breathing breathwork practice for ~10min/day over a 4-week period will lead to greater reduction in self-reported stress than practice of a placebo control breathwork practice at post-intervention.

# Secondary Hypotheses

 Coherent breathing breathwork practice for ~10min/day over a 4-week period will lead to greater reduction in self-reported stress than practice of a placebo control breathwork practice at follow-up.

- Coherent breathing breathwork practice for ~10min/day over a 4-week period will lead to greater reduction in self-reported anxiety than practice of a placebo control breathwork practice at: a) post-intervention, b) follow-up.
- Coherent breathing breathwork practice for ~10min/day over a 4-week period will lead to greater reduction in self-reported anxiety than practice of a placebo control breathwork practice at: a) post-intervention, b) follow-up.
- Coherent breathing breathwork practice for ~10min/day over a 4-week period will lead to greater reduction in self-reported depression than practice of a placebo control breathwork practice at: a) post-intervention, b) follow-up.
- Coherent breathing breathwork practice for ~10min/day over a 4-week period will lead to greater increase in self-reported well-being than practice of a placebo control breathwork practice at: a) post-intervention, b) follow-up.
- Coherent breathing breathwork practice for ~10min/day over a 4-week period will lead to greater reduction in sleep disturbance than practice of a placebo control breathwork practice at: a) post-intervention, b) follow-up.
- There will be no significant differences between intervention and placebo groups on the: a) credibility and b) expectancy of the breathwork randomly assigned to groups.

# **Exploratory Hypotheses**

Additionally, we want to see if pre-post changes are correlated with a) adherence
(amount of breathwork practice, i.e., is there a dose response?), and b)
credibility/expectancy of the breathwork intervention given. We would expect both
greater adherence(in the coherent breathwork practice arm) and
credibility/expectancy to be associated with greater improvements on the outcome
measures listed.

#### **Methods**

#### **Participants**

400 people (200 per group) will be recruited to account for potential attrition (Prolific has had up to 50% attrition rate before); 260 participants are needed based on a significance level, statistical power, and effect size of p<0.05, 0.80, and d=0.35, respectively. This builds upon our meta-analysis on breathwork and mental which found a significant small-medium effect (d=0.35), denoting breathwork was associated with lower stress. The (self-assessed) inclusion criteria are as follows: -18+ years of age (18 is the automatic minimum age on Prolific), -Able to breathe through nose, -Have access to headphones. -The following prescreeners on Prolific will also be set so only those eligible on Prolific will see the study: Located/living in UK, Fluent in English, approval rate of 98% and at least 20 previous submissions (as recommended by Prolific to increase retention and reduce dropout rates in longitudinal and multi-part studies). The (self-assessed) exclusion criteria are as follows: -Any problems which affect one's ability to pace their breathing (i.e., active/chronic respiratory infection including blocked nose/cough/cold/fever, etc.), breathlessness, cardiovascular problems, respiratory conditions or diseases (i.e., uncontrolled symptomatic asthma, COPD, lung cancer, etc.), abnormally slow breathing (bradypnea), or abnormally fast breathing (tachypnoea), -Any other physical/mental health conditions or current life events which impair or affect one's ability to engage in activities involving breath control.

# Outcome measures

All outcomes (primary, secondary, other) are mentioned below. Pre-post intervention and follow-up questionnaires will be self-completed by participants online via the survey platform Qualtrics, which will be linked to Prolific. Three short scales will be used to measure outcomes of mental health, well-being and sleep disturbance at these timepoints (baseline/pre-intervention, post-intervention, 1-month follow-up): the Depression Anxiety Stress Scale (DASS-21) (Lovibond, & Lovibond, 1995), World Health Organisation- Five Well-Being Index (WHO-5) (WHO, 1998) and PROMIS Item Bank v. 1.0 - Sleep-Related Impairment - Short Form 8a (Hanish, Lin-Dyken & Han, 2017). The primary outcome will be stress (measured using the DASS-21 stress subscale), and the primary timepoint will be postintervention (four weeks post-randomisation). The secondary outcomes will be: anxiety and depression (from DASS-21) well-being (WHO-5) and sleep disturbance (PROMIS). Immediately after starting the breathwork, participants will be asked about the credibility/expectancy of the intervention randomly allocated to them to assess if the intervention and placebo are seen as equally credible and thus merit equal expectation of benefit. This will be measured using the 6-item Credibility/Expectancy Questionnaire (CEQ) (Devilly & Borkovec, 2000), which is another secondary outcome. The last secondary outcome, which will be measured post-intervention, is: adherence (number of times participants self-reported practicing breathwork out of the 28days assigned). Other outcomes include an open-ended question on participants overall experiences of the protocol and/or study period. Pre-intervention, simple demographics (Age, Gender and Ethnicity) will be collected and, post-intervention/follow-up, participants will be asked if anything impaired their ability to perform the breathwork, and if they can guess the study hypothesis (to tentatively see if blinding was successful—see Procedure section).

# Primary Outcome Measure:

1. Subjective stress (DASS-21 stress subscale)

# Secondary Outcome Measures:

- 2. Subjective anxiety (DASS-21 anxiety subscale)
- 3. Subjective depressive symptoms (DASS-21 depression subscale)
- 4. Subjective wellbeing (WHO-5)
- 5. Subjective sleep disturbance (PROMIS-8a)

All of above outcomes measured pre-post-follow-up.

- 6. Self-reported credibility and expectancy of protocol (CEQ-6) . Measured after completing first session of breathwork.
- 7. Self-reported adherence to breathwork protocol (number of sessions participants self-report practicing out of 28 days assigned). Measured post-intervention.

Other—Overall experience, Impairment of practice, Hypothesis guessing, Attention checks
Optional open-ended questions on participants' perspectives and overall experience of the
protocol (post-intervention) / study-period (follow-up), whether anything impaired
participants' ability to perform their randomly allocated breathwork (post-intervention), and
if they can guess the hypothesis of the study (follow-up). Lastly, The DASS, WHO, and

PROMIS will all have one attention-check question in them to ensure participants are completing the surveys properly.

#### **Procedure**

Participants will be recruited entirely online via the research study platform Prolific to gain a general population sample. Participants will see a title of the study, a description (describing what participants will be doing in the study), including the participant information sheet and consent form with all key information that will help them to decide if they wish to participate. It will also be specified that the study requires audio. Participants will see all this information before they choose to take part in the study, allowing them to make an informed choice as to whether they'd like to participate. Again, pre-screeners on Prolific will also be set so only those eligible on Prolific will see the study on the platform. Participants will paid to complete the surveys at the hourly rate of 9GBP/hour (1.50GBP per survey, so 4.50GBP in total) which is deemed as a good, recommended amount by Prolific. We unfortunately do not have funds to pay participants to complete the daily breathwork (classed as low effort activity by Prolific). Daily reminder messages will be sent through Prolific to practice breathwork over the 28days/4weeks and keep a record of number of times practiced. All participant data will be anonymous (only Prolific user IDs will be seen). No identifiable personal information will be collected. When the first (pre-intervention) survey is complete we will get the participant IDs of the relevant Prolific participants. We will then invite these participants to postintervention and follow-up surveys using a custom allowlist on Prolific. As we have two conditions and want to keep these conditions consistent between surveys, a separate identical CEQ, post-intervention and follow-up survey for each condition is set up. However, only one pre-intervention survey is needed as Qualtrics supports allocation to conditions from one URL. Messages will also be sent through Prolific to complete post-intervention and follow-up questionnaires when required.

# Intervention and Comparator

Both groups will also be provided with an identical ~5min introductory/welcome audio to the study which they can listen to on the first day.

Participants in intervention group will be randomised to a guided audio of coherent breathing (at ~5.5.bcpm with equal inhales/exhales of ~5.5secs each without deliberate pauses), for 28days (4weeks), pre-recorded by a trained breathwork facilitator, delivered remotely online. The average coherent breathing rate for maximising HRV is around 5.5bcpm so this cadence was chosen for the intervention group. The duration of ~10min was deemed as a manageable time for participants, and several studies (ranging from days to weeks) on meditation have shown benefit can be derived from this short length of practice.

Participants in control group will be randomised to a guided audio of placebo 'sham' coherent breathing breathwork (12bcpm with equal inhales/exhales of 2.5secs each without deliberate pauses) for ~10mins/day, for 28days (4weeks), pre-recorded by a trained breathwork facilitator, delivered remotely online. The metric of 12bcpm is in line with guidance from the British Journal of Nursing, Royal College of Physicians, and Johns Hopkins University which state that the average, healthy bcpm should range from: 12-18bcpm, 12-20bcpm, and 12-16bcpm, respectively, hence we chose the minimum for the control group.

12 bcpm is highly unlikely to be difficult or detrimental to anyone based on BJN, RCP, and JHU guidance as it is at the lower bound of bcpm for typical resting breathing for adults.

The intervention/control audios are identical (exact same sound and instruction). The placebo control is matched to the active intervention in all domains but pace of breathing.

### Randomisation and blinding

The type of study is participant blinded RCT with assessor blinded data collection (that is assessor is not present for data collection which is self-completed by the participant on a survey software platform). After completing the pre-intervention survey, participants will be randomly assigned, via the online survey software Qualtrics using block randomisation (1:1), to receive either the intervention coherent breathing breathwork (5.5bcpm), or placebo coherent breathing breathwork (12bcpm). Participants will be blinded to their intervention (concealment)—the technique of breathwork will be referred to as 'rhythmic breathing' in both the active intervention and placebo control breathwork audios, in an attempt to blind participants to the intervention being used.

# Safety and ethical considerations

This study has been approved by the Research Ethics Committee at the University of Sussex Sciences & Technology C-REC (reference: ER/GF221/2).

Statistical analysis plan (SAP)

Effects of coherent breathing breathwork on mental health and wellbeing: A randomised placebo-controlled study (NCT05676658)

[name], [name], [name]

Document date: March 15, 2023

Outcome scale measures (quantitative): Stress, anxiety, depression, well-being, sleep disturbance, credibility/expectancy of breathwork

Primary outcome of stress at post-intervention (primary timepoint) will be calculated from Depression Anxiety Stress Scale—21 items (DASS-21) stress subscale. Secondary outcomes of stress (at follow-up), anxiety and depression will be calculated from their respective DASS-21 subscales. The scores on DASS-21 subscales will be multiped by two to convert them to scores equivalent to the longer form DASS-42 score in line with scoring recommendations. Secondary outcomes of well-being and sleep disturbance will be measured by the World Health Organisation—Five Well-Being Index (WHO-5) and PROMIS Item Bank v. 1.0 - Sleep-Related Impairment—Short Form 8a, (PROMIS-8a) respectively. PROMIS-8a will be scored using a T-score transformation according to PROMIS Sleep scoring manual. Pre-intervention, post-intervention (after 28 days) and follow-up (after a further 28 days) scale score differences between groups will be analysed through mixed analysis of variance.

Self-reported credibility and expectancy of the breathwork protocol will be measured via the Credibility/Expectancy Questionnaire (CEQ-6). Descriptive statistics for all measures for all participants in each condition will be reported. Missing items within scales will be replaced using the mean for other items in the scale/subscale in cases where = <30% of items are missing for a scale/subscale. Multiple imputation will be used where >30% of data is missing from a scale/subscale or where whole scales/subscales are missing. Cronbach's alphas will be used to assess internal consistency of each scale at baseline.

Primary analysis

Intention-to-treat; using an independent t-test to see if there is a difference. Post-intervention is the primary timepoint for primary outcome stress. For both the primary outcome and secondary scale outcomes, group x time effects at the p<.05 level will be determined using mixed ANOVAs. Group x time effects at the p<.05 level will be followed up with simple contrasts (with pre-intervention as the comparator) and Bonferroni-corrected within-group t-tests. Baseline data will be controlled for depending on the outcome being tested (i.e., DASS Stress at baseline will be entered as a covariate when testing effects on DASS Stress). Data analysis will be performed in R and SPSS.

Secondary analysis

Per-protocol analysis (participants completing at least 14 sessions [50%] of the breathwork) will be conducted as secondary analysis.

Sensitivity checks

If sizeable missing data are present (greater than 5%), they will be replaced using multiple imputation, and used for sensitivity analysis. Analysis without baseline covariates will be included as sensitivity analysis. The DASS, WHO, and PROMIS all have one attention-check question in them to ensure participants are completing the surveys properly. If a participant answers more than one incorrectly at each timepoint their data will be excluded from the main analyses but included in a sensitivity analysis. The same applies to those who state that their breathwork practice was significantly impaired in response to the question on impairment of practice below.

Exploratory analysis of secondary measures (quantitative)

Adherence to breathwork protocol

Post-intervention, participants will answer how many times they completed the guided breathwork out of the assigned 28 days. This will be compared between groups via unpaired t-test, and correlated with outcome scale scores on DASS, WHO and PROMIS within each condition to see whether there are any associations between adherence and changes in these scale scores. Adherence will be looked at as a moderator.

Credibility/expectancy of breathwork protocol

Similar to adherence, CEQ scores will be correlated with the outcome scale scores above, to see whether there are relationships between CEQ and changes in these scale scores within each condition. CEQ scales will be compared between groups via unpaired t-tests. If there are significant differences between groups on credibility/expectancy, it will be used in covariance analysis.

Other complementary outcomes (qualitative)

Three simple qualitative outcomes will be explored to offer complementary findings to the main quantitative analyses above.

Overall Experience

Optional open-ended questions on participants' perspectives and overall experience of the protocol/study-period (i.e., anything positive, negative, neutral, general notes, etc.) post-intervention and follow-up. Analysis will be simple content analysis.

Impairment of Practice

Optional open-ended question on whether anything impaired participants' ability to perform their randomly allocated breathwork at post-intervention. Participants can answer yes/no and provide free text. The yes/no questions can be coded and free text analysed through simple qualitative content analysis.

Hypothesis Guessing

Optional open-ended question on whether participants can guess the hypothesis of the study at follow-up, to tentatively infer if blinding was successful. Participants can answer yes/no and provide free text. The yes/no questions will be coded and free text checked to see if guess was correct.

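### The SAP names both a t-test and a three-timepoint group x time ANOVA for the primary outcome, does not say which decides, and leaves the baseline adjustment undefined

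*SAP*

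**What the plan says.** The protocol (Primary hypothesis; Outcome measures) and the SAP agree on the target: DASS-21 stress at post-intervention. The statements on how to test it are these.

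- SAP, Primary analysis, first sentence: intention-to-treat, "using an independent t-test to see if there is a difference". The variable (post-intervention score or change) is not named.
- SAP, Primary analysis: "For both the primary outcome and secondary scale outcomes, group x time effects at the p<.05 level will be determined using mixed ANOVAs".
- SAP, outcome scale paragraph: scores at pre-intervention, post-intervention and follow-up enter that model, and "scale score differences between groups will be analysed through mixed analysis of variance". The same paragraph classes follow-up stress as secondary: "Secondary outcomes of stress (at follow-up), anxiety and depression will be calculated from their respective DASS-21 subscales".
- SAP, Primary analysis: group x time effects at the 5% level "will be followed up with simple contrasts (with pre-intervention as the comparator").
- SAP, Primary analysis, on baseline: "DASS Stress at baseline will be entered as a covariate when testing effects on DASS Stress".
- SAP, Sensitivity checks: "Analysis without baseline covariates will be included as sensitivity analysis".
- Protocol, Participants: "260 participants are needed based on a significance level, statistical power, and effect size of p<0.05, 0.80, and d=0.35, respectively".

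No sentence ranks the t-test against the ANOVA, and none gives the model that the baseline covariate enters.

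**The concern.** There are three linked problems.

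**No deciding test.** Two tests with different hypotheses sit under one heading. An independent t-test takes no covariate. Read with the covariate sentence and the sensitivity sentence, the test named first, which is also the one that was powered, becomes a sensitivity analysis.

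**The interaction test is not about the primary timepoint.** With three visits it has 2 degrees of freedom and pools the primary outcome with one the SAP calls secondary. It can be significant with no effect at post-intervention. On this route the pre-to-post contrast is reached only after the interaction is significant.

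**Baseline has up to three roles.** It is a level of time, the comparator of the contrasts and, on the direct reading, a covariate in the same model. As a main-effect covariate it leaves the group x time term unchanged, so the adjustment achieves nothing. With a covariate x time term the model forces the baseline group difference to zero, and the post-versus-pre contrast becomes the ANCOVA. The SAP does not say which applies.

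At stake is whether the primary conclusion is fixed before the data are seen.

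**Working it through.** **Inputs.** From the protocol: d=0.35, two-group alpha 0.05, power 0.80, total 260, 1:1 allocation. Assumed, because the documents give no values: SD 1, normal scores, complete data, and one common correlation r between any two visits, taken as 0.4/0.5/0.6 (0.3 and 0.7 where stated).

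**1. Which test gives 260?** For a two-sided independent t-test with n per arm, the noncentrality is d·√(n/2). At n=130 this is 0.35 × √65 = 2.822 on 258 df, giving power 80.3%. The exact requirement is 129.1, so 130 per arm and 260 in total. A one-sided test would need about 102 per arm. The 260 is therefore the size for a two-sided, unadjusted comparison at one timepoint.

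**2. What does the interaction test respond to?** Let the group differences at the three visits be δ = (pre, post, follow-up). The noncentrality of the interaction F on 2 and 2 × 258 = 516 df is λ = (n/2) · Σ(δ − mean δ)² / (1 − r).

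| True effect | δ | Σ(δ − mean)² | λ at r=0.4/0.5/0.6 | Power |
|---|---|---|---|---|
| Post and follow-up | (0, 0.35, 0.35) | 0.0817 | 8.85/10.62/13.27 | 76/84/91% |
| Follow-up only | (0, 0, 0.35) | 0.0817 | 8.85/10.62/13.27 | 76/84/91% |
| Post, halved by follow-up | (0, 0.35, 0.175) | 0.0613 | 6.64/7.96/9.95 | 63/71/81% |

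The first two rows are identical: the test cannot tell an effect present at post-intervention from one absent there. Simulation (10,000 replicates per scenario) gave 76/84/91%, 76/83/91% and 62/71/81%. A separate simulation at r=0.3/0.7 gave 69%/97% for the sustained effect.

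**3. Interaction first, then the pre-to-post contrast (simulated).** With a sustained d=0.35, both steps succeed in 68/76/85% of trials. If the effect halves by follow-up, the figure is 60/70/80%. With an effect at follow-up only it is about 5%, and with no effect about 2.6%.

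**4. Baseline-adjusted comparison at post-intervention.** ANCOVA has effective size d/√(1 − r²). This is 0.382/0.404/0.4375; multiplied by √65 it gives noncentralities 3.08/3.26/3.53 and power 87/90/94% at 130 per arm. The number needed for 80% is 129.1 × (1 − r²) = 108.4/96.8/82.6, so about 109/97/83 per arm.

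**5. Error rate with no effect (simulated, 20,000 replicates).**

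| Rule for success | Rejections at r=0.4/0.5/0.6 |
|---|---|
| Any one test, named in advance | 5% |
| t-test or interaction | 9.1/9.3/9.3% |
| t-test, interaction or ANCOVA | 10.1/10.5/10.6% |
| t-test, or interaction followed by post contrast | 6.9/7.1/7.0% |

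**6. How often does the choice matter?** With a sustained d=0.35, the t-test and the interaction reach different conclusions in 32/26/21% of trials at r=0.3/0.5/0.7.

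**7. The covariate readings in one simulated dataset (r=0.5).**

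| Analysis | Estimate | SE |
|---|---|---|
| t-test at post | −0.333 | 0.119 |
| ANOVA post-versus-pre contrast | −0.390 | 0.115 |
| Same, baseline added as a main effect | −0.390 | 0.115 |
| Same, with covariate x time | −0.366 | 0.098 |
| ANCOVA at post | −0.366 | 0.098 |

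The SAP's wording allows these three different answers from the same data.

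**The case against.** The strongest reply is that the t-test comes first, stands next to the sentence naming the primary timepoint, and reproduces the sample size exactly, so a reader would take it as decisive. On that reading alpha and power are as planned. The covariate sentence follows the ANOVA sentences, so the line demoting unadjusted analyses may concern only the ANOVA. This is a fair inference, but the SAP does not state it, and the ANOVA sentence explicitly includes the primary outcome.

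Second, the simple contrasts locate the effect, and post-versus-pre matches the primary hypothesis. That stands: the two-step route does not inflate error (about 2.6% under the null, about 5% with an effect at follow-up only). Its cost is the dependence on the interaction, which lowers power in most of the scenarios shown.

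Third, the SAP nowhere says that a win on either test would count, so the 9 to 10% figures describe a rule it does not contain. That is right. They show what the silence permits, and the concern does not rest on them.

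Fourth, an unadjusted t-test in a randomised trial is valid, so ANCOVA is a gain in efficiency and not the correction of an error. This also stands. Naming the t-test alone would settle which test decides.

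Finally, the covariate itself is named. What is missing is the model it enters.

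**Conclusion.** The concern holds. The contradiction is in the SAP's own text and needs no simulation: two tests for one primary outcome, no ranking, a powered test that sits among the sensitivity analyses on the plain reading, and a covariate without a model.

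The consequence depends on the reading. If the t-test alone decides, the design performs as planned but forgoes 7 to 14 percentage points of power (80% against 87/90/94%). If the interaction alone decides, a positive result need not concern post-intervention, and power for d=0.35 runs from about 62% to 91% across the scenarios at r=0.4 to 0.6. If the contrast must wait for the interaction, power is 60 to 85%. If either test counted, the error rate would be about 9%.

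These sizes rest on assumed correlations, compound symmetry, normality and complete data. The ambiguity does not. It bears on the trial's main conclusion and should be settled before outcome data are examined.

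**What to change.** Amend the SAP's Primary analysis section as follows.

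- **Primary test:** ANCOVA of DASS-21 stress at post-intervention on arm, with baseline stress as covariate, two-sided at 5%. Report the adjusted mean difference and 95% confidence interval. State that it does not depend on the group x time test.
- **Unadjusted t-test at post-intervention:** label it sensitivity, which agrees with the existing Sensitivity checks sentence.
- **Longitudinal model:** make it secondary, with post-intervention and follow-up as the only outcome levels and baseline and baseline x time as covariates. Report the arm difference at each visit. The post-intervention estimate will be close to the ANCOVA, but not identical when post-intervention data are missing.
- **Within-group tests:** label them descriptive.
- **Sample size:** state that 260 was derived for the unadjusted two-sided t-test and is sufficient for the ANCOVA.

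If the sponsor prefers the t-test as the single primary test, naming it and its variable resolves which test decides, without the gain in power. The SAP must then also say that the sensitivity sentence does not apply to it.

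The cost is SAP wording only. Baseline stress is already collected, and no extra participants, visits or data are needed.

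### The SAP does not name the test that decides each timepoint hypothesis, and the within-group t-tests it lists cannot support a claim of benefit over placebo

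*SAP*

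**What the plan says.** The protocol's primary hypothesis is a between-arm claim at one timepoint: "greater reduction in self-reported stress than practice of a placebo control breathwork practice at post-intervention". The secondary scale hypotheses take the same form. Stress at follow-up is one of them. Anxiety, depression, well-being and sleep disturbance are each compared with placebo "than practice of a placebo control breathwork practice at: a) post-intervention, b) follow-up".

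The SAP's Primary analysis section contains these steps:

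- It opens with a between-arm test: "Intention-to-treat; using an independent t-test to see if there is a difference". No timepoint is attached, but the next sentence reads "Post-intervention is the primary timepoint for primary outcome stress".
- For the primary and secondary scale outcomes, "group x time effects at the p<.05 level will be determined using mixed ANOVAs". Time has three levels: pre-intervention, post-intervention and follow-up.
- A significant interaction "will be followed up with simple contrasts (with pre-intervention as the comparator) and Bonferroni-corrected within-group t-tests".
- Baseline is also a covariate: "DASS Stress at baseline will be entered as a covariate when testing effects on DASS Stress".

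The SAP does not define the simple contrasts as between-arm or within-arm. It does not say which result settles each hypothesis, or whether the within-group tests are only descriptive.

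**The concern.** An interaction over three timepoints shows that the arms' profiles differ somewhere, but not where. The hypotheses are specific to a timepoint, so the follow-up tests have to locate the effect. One of the two tools named for this compares an arm with its own baseline.

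That comparison cannot isolate benefit over placebo. The trial has no arm without practice. The sham is itself guided daily paced breathing, set at the bottom of the quoted resting range (Protocol, Intervention and Comparator: "hence we chose the minimum for the control group"). Change within either arm therefore includes natural course, repeat testing and non-specific benefit. A significant result in the coherent arm beside a non-significant one in the placebo arm does not show that the arms differ.

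The SAP names no explicit between-arm test for stress at follow-up, or for the four secondary scale outcomes at either timepoint, unless the simple contrasts are that test. That leaves 1 + 4 x 2 = 9 hypotheses without a clearly named deciding test. If the interaction is driven by one timepoint, the within-group results at the other could be read as a treatment effect there. They could also contradict a between-arm contrast, with no rule for choosing between the two.

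**Working it through.** **1. What the trial is sized for.** The protocol (Participants) gives 260 for p<0.05, power 0.80 and d=0.35. Two-sided, n per arm = 2 x (1.960 + 0.842)^2 / 0.35^2 = 128.1, so 129 per arm and 258 in total. The exact t-test solution is 129.1, so 130 per arm and 260. A one-sided test would need 202. The stated figure is therefore that of a two-sided between-arm comparison.

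**2. Inputs.** From the documents: 130 per arm (260/2), effect 0.35 SD, interaction test at 0.05. Assumed, because the documents do not give them: correlation 0.6 between any two timepoints, four within-group tests per outcome (two arms x two timepoints, each at 0.05/4 = 0.0125), a true effect at post-intervention only, and equal natural improvement m in both arms at both later timepoints, from 0 to 0.4 SD.

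**3. Power of one within-group test at follow-up.** The SD of a change score is sqrt(2 x (1 - 0.6)) = 0.894, so its standard error is 0.894/sqrt(130) = 0.0784. The critical t at 0.0125 with 129 df is 2.533. Noncentrality is m/0.0784. With no true effect at follow-up, both arms have the same power p. The arms are independent, so the chance that coherent is significant and placebo is not is p(1 - p).

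| m (SD) | Noncentrality | p | p(1 - p) |
|---|---|---|---|
| 0 | 0 | 0.0125 | 1.2% |
| 0.1 | 1.27 | 0.108 | 9.6% |
| 0.2 | 2.55 | 0.508 | 25.0% |
| 0.3 | 3.82 | 0.900 | 9.0% |
| 0.4 | 5.10 | 0.994 | 0.6% |

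**4. After a significant interaction.** Simulating the three timepoints and keeping only trials that pass the mixed-ANOVA interaction test (about 91% of them) gives nearly the same values:

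| m (SD) | Arms' within-group tests disagree, either direction | Coherent significant, placebo not |
|---|---|---|
| 0 | 3% | about 1% |
| 0.1 | 20% | about 10% |
| 0.2 | 52% | about 25% |
| 0.3 | 19% | about 10% |
| 0.4 | 1% | about 1% |

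A two-sided between-arm test of change at follow-up, in the same trials, is significant in 5-6%. At m = 0.2, correlations of 0.5 to 0.7 give 45-52% for disagreement and 23-26% for coherent only.

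**5. No effect at any timepoint.** The interaction test passes in about 5% of trials whatever the natural improvement, so the within-group tests are rarely reached.

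**6. The opposite error.** At post-intervention, where the assumed effect of 0.35 SD is real, the pattern of coherent significant and placebo not appears after a passed interaction test in 48% of all trials at m = 0.2 and 10% at m = 0.3. The between-arm contrast finds the effect in 86% and 84%. The within-group pattern therefore follows natural change more than the treatment effect.

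**The case against.** The strongest reply is that the between-arm answer is already in the plan. Simple contrasts against pre-intervention, run as group x time contrasts, are exactly the between-arm tests at post-intervention and follow-up. The SAP's opening section also describes the mixed ANOVA as analysing differences between groups. Nothing says that the within-group tests decide a hypothesis, and they are Bonferroni-corrected and run only after a significant interaction. Much of this stands, and it limits the point. It does not remove it, because the SAP leaves the contrasts undefined and names no deciding result. Using baseline both as a level of time and as a covariate also blurs what a contrast against pre-intervention means.

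Four stronger readings are tempting, and the documents do not support them:

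- **The primary hypothesis is exposed.** The independent t-test appears to cover stress at post-intervention, although its timepoint is only implied.
- **Equal improvement in both arms would be reported as proof that breathwork works.** When the arms differ at no timepoint, the interaction test stops this in about 95% of trials. The SAP makes no such claim either. The risk remains only where the arms differ at one timepoint and match at the other.
- **The error is about 50%.** That is the peak of disagreement in either direction, reached when each within-group test has about even power. About half of it is placebo-only significance, which would not support the hypothesis.
- **False support at follow-up is 46-82%.** This arises at 0.2-0.3 SD natural improvement only if significance in the coherent arm alone decided the hypothesis. The SAP states no such rule, and the figure is 0.6% with no natural change.

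**Conclusion.** The point holds as a gap in specification, with one listed procedure that does not fit the hypotheses. For stress at follow-up and the four secondary scale outcomes at both timepoints, the SAP names no deciding test, and the within-group t-tests cannot fill that place.

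The size depends on natural improvement, which the documents do not give. Under the assumptions above, the misleading pattern at follow-up ranges from about 1% to about 25% of trials with a significant interaction, peaking near 0.2 SD. At 0 and 0.4 SD it falls below the 5-6% of a between-arm test. The argument therefore does not rest on the peak. The within-group pattern has no controlled error rate for the question asked, whereas the between-arm test holds its rate throughout. The sample size is unaffected.

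**What to change.** In the SAP's Primary analysis section:

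1. State that each scale hypothesis is judged by the between-arm difference, adjusted for the baseline score, with its 95% CI, at post-intervention and at follow-up.
2. Define any simple contrasts as group x time contrasts, meaning the difference between arms in change from pre-intervention, and say that they support this estimate and do not compete with it.
3. Replace the within-group t-tests with descriptive within-arm changes, without p-values.

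This changes SAP wording only. It needs no new data and no change in sample size, and the baseline adjustment is already planned. The cost is that improvement within an arm can no longer be reported as a tested finding.
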